## **10.3.** Lost to Follow-up

A subject will be considered lost to follow-up for failure to complete the safety follow-up assessment 30 days after the last dose of study drug (up to Study Day 51 with a +7-day window).

The following actions must be taken if a subject fails to complete the required safety follow-up assessment 30 days after the last dose of study drug (up to Study Day 51 with a +7-day window):

- The site must attempt to contact the subject and reschedule the missed visit as soon as possible, counsel the subject on the importance of final study assessments, and ascertain whether the subject wishes to and/or should continue in the study.
- Before a subject is deemed lost to follow-up, the investigator or designee must make every effort to regain contact with the subject (where possible, 3 telephone calls and, if necessary, a certified letter to the subject's last known mailing address or local equivalent methods). These contact attempts should be documented in the subject's medical record.
- Subjects who continue to be unreachable will be considered to have withdrawn from the study.

Closure of specific sites or of the study as a whole are described in Section 13.1.7.

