## 6.2.2. Secondary Objective Endpoints

- Hospital length of stay (measured in days)
- Any-cause mortality (measured from beginning of treatment until the safety follow-up assessment 30 days after last study treatment [up to and including Study Day 51 with a +7-day window])
- SOFA score
- Total duration of mechanical intervention (measured in days)
- Total duration of oxygen therapy (by continuously worn mask or nasal cannula, measured in days)
- APL-9 PK parameters
- Observed values and changes from baseline in markers of complement activation (C3, C3a, C4, C4a, Bb, C5a, TCC, and alternative complement pathway hemolytic activity [AH50]), coagulopathy (reticulocyte count, schistocytes, lactate dehydrogenase, D-dimer, ferritin, haptoglobin, and fibrinogen), and inflammatory cytokines (C-reactive protein [CRP], tumor necrosis factor α [TNFα], IL-1β, and IL-6).

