## Part 2 (Randomized Double-Blind Period):

Part 2 of the study will be initiated only upon recommendation from the DMC. Required criteria for initiation of Part 2 will include (1) no fatal/life-threatening SAEs thought possibly related to APL-9 by the DMC, and (2) no more than 1 subject requiring premature treatment discontinuation by the investigator due to AEs or abnormal laboratory tests. All subjects will receive SOC independent of their randomization. Approximately 60 subjects will be randomly

assigned in a 1:1 ratio to blinded treatment with either APL-9 or saline vehicle. Subjects will receive treatment with APL-9 or vehicle from Day 1 through Day 7, discontinuation of respiratory support (supplemental oxygen or mechanical ventilation), or hospital discharge, whichever occurs latest.

Subjects may receive treatment beyond Day 7 if the DMC approves an extended treatment duration following the review of data from Part 1 or during the conduct of Part 2. The DMC may approve any extended treatment duration up to and including Day 21; extended treatment will be allowed only in subjects who still require respiratory support (oxygen supplementation or mechanical ventilation) at Day 7 with an improved PaO2/FiO2 ratio of at least 20 mm Hg from baseline if arterial blood gas (ABG) test results are available for comparison. If ABG test results are not available, an improvement in FiO2 of at least 4% in nonventilated patients (eg, those on nasal cannula) and 10% in mechanically ventilated patients is needed. FiO2 should be weaned following the site's protocol to keep oxygen saturation at 89% or above. Treatment beyond Day 7 and through any DMC-approved extension will be at the discretion of the investigator. Treatment beyond Day 7 and up to and including any DMC-approved extension will be at the discretion of the investigator.

Follow-up safety assessments for each subject will be collected 30 days following the last dose of study treatment (up to and including Study Day 51 with a +7-day window). Safety assessments may be performed any time during the 30-day follow-up period at the investigator's discretion but are required 30 days after the last dose of study drug (up to and including Study Day 51 with a +7-day window). These assessments will be conducted via inpatient assessment (for subjects still hospitalized) or by telephone call (for subjects discharged).

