- i The concomitant procedures include recording the day that the subject was admitted to the ICU (or ICU-type environment), use of ventilatory support, use of oxygen therapy, date of ICU discharge, date of hospital discharge, and survival. The time and date of any changes to concomitant medications and procedures are to be recorded at the days indicated in the schedule of assessments. In case of early hospital discharge, the data is collected via phone interviews.

#### APL-9 APL9-COV-201 Protocol Amendment 3

- j Infusion-related reactions that occur during the administration of the 50-mL loading dose should be treated as follows: For mild infusion-related reactions: The 50-mL bag infusion time should be increased from 10 min to 20-40 min and the reaction should be monitored. Treatment with diphenhydramine may be required. The infusion time of the 250-mL bag should not be increased. For severe or persistent mild infusion-related reactions (instances in which the subject's symptoms do not respond to the increased infusion time), treatment should be discontinued, and the institution's emergency hypersensitivity protocol should be employed. Refer to the procedure for handling infusion-related reactions in Section 9.1.1.
- k Confirmation of SARS-CoV-2 infection for screening may be completed more than 7 days before baseline.
-  Vaccination history should be attempted to be collected as a component of medical history.
- m A PK/PD assessment will be done on the last day of treatment. If EOT and discharge day visit are on different days, a PK/PD sample will be collected on the discharge day as an unscheduled visit.
- n If EOT and day of discharge visit are on different days, perform EOT assessments on the last day of treatment and repeat on the day of discharge as an unscheduled visit. Perform/record vital signs, ECG, concomitant medications/procedures, infusion site reactions, and AEs daily up to and including day of discharge. After EOT, record as unscheduled visits.

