6.2 Analysis of Secondary Efficacy Endpoints

6.2.1 Time-to-event endpoints

The following time-to-event endpoints are defined as:

- Hospital length of stay: initiation of study drug (Day 1, for Part 1) or randomization date (for Part 2) to hospital discharge. For subjects with death of any cause or withdrawal of study participation, hospital length of stay will be imputed with the longest hospital length of stay observed in the study.
- Overall survival: initiation of study drug (Day 1, for Part 1) or randomization date (for Part 2) to death of any cause; censored at the last day known to be alive.
- Total duration of mechanical ventilation defined as days on mechanical ventilation during the study participation, calculated as follows:
 - For subjects with death of any cause (or withdrawal of study participation), total duration of mechanical ventilation will be imputed with the longest duration observed in the study.
 - For any subject who is on mechanical ventilation at the initiation of study drug (Day 1, for Part 1) or at the randomization date (for Part 2), total duration of mechanical ventilation is calculated from Day 1 or randomization date.
 - For any subject who is not on mechanical ventilation at the initiation of study drug (Day 1, for Part 1) or at the randomization date (for Part 2), patient will be excluded.
- Total duration of oxygen therapy defined as days on mechanical ventilation or supplemental oxygen during the study participation, calculated as follows:

- For subjects with death of any cause (or withdrawal of study participation), total duration of oxygen therapy will be imputed with the longest duration observed in the study.
- For any subject who is on mechanical ventilation or supplemental oxygen at the initiation of study drug (Day 1, for Part 1) or at the randomization date (for Part 2), total duration of oxygen therapy is calculated from Day 1 or randomization date.
- For any subject who is not on mechanical ventilation or supplemental oxygen at the initiation of study drug (Day 1, for Part 1) or at the randomization date (for Part 2), patient will be excluded.

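### No vital-status check is required before an unreachable subject is classed as withdrawn, so a death the site never learns of lowers recorded mortality and drops out of the primary safety endpoint

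*Protocol*

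**What the plan says.** Any-cause mortality, counted from first treatment to the safety assessment 30 days after the last dose, is a secondary endpoint (Protocol 6.2.2, SAP 2.2.2). The primary endpoint is the cumulative incidence of treatment-emergent adverse events and serious adverse events (Protocol 6.2.1), collected up to the same assessment (Protocol 11.2.5 and 12.4).

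Protocol 7.1 has subjects still in hospital assessed there and discharged subjects telephoned. Before the required 30-day contact, follow-up is optional: "Safety assessments may be performed any time during the 30-day follow-up period at the investigator's discretion". Table 1 footnote i lists survival among the items to be recorded and adds: "In case of early hospital discharge, the data is collected via phone interviews".

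If the 30-day assessment is missed, Protocol 10.3 says that "the investigator or designee must make every effort to regain contact with the subject" and describes the means as "where possible, 3 telephone calls and, if necessary, a certified letter to the subject's last known mailing address or local equivalent methods". The end of the process is: "Subjects who continue to be unreachable will be considered to have withdrawn from the study".

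SAP 6.2.1 measures overall survival from the start of study drug (Part 1) or randomization (Part 2) "to death of any cause; censored at the last day known to be alive". For hospital stay and for duration of ventilation and of oxygen, the same section gives subjects who die or withdraw the longest value seen in the study.

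**The concern.** The duty in 10.3 is to regain contact with the subject, not to establish whether the subject is alive. No relative or other secondary contact, treating physician, hospital record or death record is named in either document. Death is itself a cause of non-response, so the subjects lost in this way are not a random sample of those discharged. Kaplan-Meier, log-rank and Cox methods assume non-informative censoring. Here that assumption fails in a known direction, and recorded mortality is too low.

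The primary endpoint is affected as well. An unlearned death after discharge is a fatal serious adverse event inside the collection window that is never counted. No later analysis can recover it.

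The withdrawn label has a further effect. Read literally, SAP 6.2.1 would replace the known hospital stay of a discharged subject who later cannot be reached with the longest stay in the study. That subject would be a worst case for hospital stay and a censored observation for survival.

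**Working it through.** **1. The plan's own figures.** Protocol 12.1 gives the chance of at least one reported serious adverse event with 30 subjects as 26%, 71% and 89% at true incidences of 1%, 4% and 7%, and above 95% at 10%. The formula 1 - (1 - p)^30 gives 26.0%, 70.6%, 88.7% and 95.8%, so the figures reproduce. They take every event that occurs to be reported. If only a share c of some event type is captured, the formula becomes 1 - (1 - pc)^30. At p = 4% this is 59.9% for c = 75% and 45.5% for c = 50%. Those values of c are stress values. They apply only to an event type of which that share is lost, not to serious adverse events in general.

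**2. Effect of one missed death.** One death in 30 is 1/30 = 3.3 percentage points. For Kaplan-Meier, assume 4 of 30 die in hospital, 26 are discharged and 2 of those die later, with missed deaths censored at discharge.
- None missed: 6/30 = 20.0%.
- One missed: 1 - (26/30) × (24/25) = 16.8%.
- Both missed: 1 - 26/30 = 13.3%.

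Censoring instead of counting the subject as alive makes almost no difference: 16.8% against 5/30 = 16.7% with one death missed.

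**3. How likely a missed death is.** The documents give no discharge share, post-discharge risk or ascertainment rate, so all three are assumptions. Take 25 of 30 per arm discharged alive (50 in total), post-discharge death risk p, and probability u that the site never learns of a death. The chance of missing at least one is 1 - (1 - pu)^50, and the expected number missed is 50pu.

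| p | u | Chance of missing at least one | Expected missed, both arms |
|---|---|---|---|
| 2% | 10% | 9.5% | 0.1 |
| 4% | 10% | 18% | 0.2 |
| 2% | 50% | 39% | 0.5 |
| 4% | 70% | 76% | 1.4 |
| 6% | 70% | 88% | 2.1 |

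**4. Difference between arms.** Assume 90% of one arm and 70% of the other are discharged, with equal risks. The difference in expected missed deaths is 30 × (0.9 - 0.7) × p × u. For p from 2% to 10% and u from 25% to 100%, this runs from 0.03 to 0.6 deaths.

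The time at risk after discharge also matters. The follow-up clock starts at the last dose. If dosing stops at discharge or at the maximum day, whichever is first (one reading of Protocol 10.1), a Day 7 maximum gives 30 days from discharge to follow-up for discharge on Day 4, 6 or 7, then 27 days for Day 10, 23 for Day 14 and 17 for Day 20. With treatment extended to Day 21, it is 30 days for any discharge up to Day 21. Earlier discharge lengthens the window only when discharge falls after the last dose.

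**The case against.** Protocol 10.3 does not forbid other routes. It asks for every effort and allows local equivalents, and a household member may answer a call or a letter. Footnote i does not say who is interviewed. Some subjects have a legally authorized representative known to the site, interim contacts are allowed, and subjects who stop early because of an adverse event are followed until it resolves or stabilizes. The survival rule in SAP 6.2.1 does not depend on the withdrawn label: a death learned by any route already counts as an event. Mortality is also secondary, in a Phase 1/2 study with no primary efficacy endpoint.

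All of this stands. It limits the point to deaths the site never learns of, and it means that high values of u cannot be taken for granted. It does not supply the missing step, because what is permitted may be done at one site and not at another.

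A reader might infer that losses fall mostly in the arm that leaves hospital sooner, so that this arm looks better on survival. The documents do not support that. The post-discharge window can be the same in both arms, and a lower post-discharge risk in the faster arm could reverse the direction. An example with 6 deaths per arm, 2 of them after discharge in one arm only, does not show it either. It has nearly equal numbers discharged (26 and 24) and simply assumes post-discharge mortality of 2/26 = 7.7% against 0/24.

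**Conclusion.** The point holds in a limited form. The plan requires no vital-status check before a subject is declared lost. A post-discharge death that is never learned of is therefore informatively censored in overall survival and missing from the primary safety endpoint. The bias in recorded mortality is downward, at about 3 percentage points per missed death in an arm of 30.

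The number missed rests wholly on assumptions. The chance of at least one ranges from about 10% where ascertainment is good to 88% at the pessimistic end, and 0.1 to 2.1 deaths are expected across both arms. An imbalance between arms is possible, under one death on the ranges tried, and its direction is unknown. This is a cheap improvement worth making, not a flaw that undermines the design.

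**What to change.** In Protocol 10.3, before a subject is declared lost, require one documented vital-status check. Acceptable sources would be the site or hospital record, a secondary contact or legally authorized representative recorded at consent or discharge, the treating physician, or a public death record where permitted. Record dead or alive with the date, even if nothing else can be collected. Exclude subjects who withdrew consent for future information.

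In SAP 6.2.1, state that this date serves as the date of death or of last known survival. This mainly clarifies the existing rule.

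Separate lost to follow-up from withdrawn in both documents, so that the longest-value imputation does not overwrite a hospital stay that is already known. Reporting the number with unknown vital status by arm would let readers judge any imbalance.

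The cost is one contact field, a few sentences in the protocol and SAP, and consent and privacy wording, which may need local adaptation.

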## 11. STUDY ASSESSMENTS AND PROCEDURES

- Day 1 is defined as the day upon which study treatment is first administered.
- The last predose assessments will be considered as baseline assessments.
- Study procedures and their timings are summarized in the SoA (Table 1). Protocol waivers or exemptions are not allowed.
- Significant safety concerns should be discussed with the sponsor immediately upon occurrence or awareness to determine whether the subject should continue or discontinue study participation.
- Adherence to the study design requirements, including those specified in the SoA (Table 1), is essential and required for study conduct.
- All screening evaluations must be completed and reviewed to confirm that potential subjects meet all eligibility criteria. The investigator will maintain a screening log to record details of all subjects screened and to confirm eligibility or record reasons for screening failure, as applicable.
- Procedures conducted as part of the subject's routine clinical management and obtained before signing of the informed consent form (ICF) may be utilized for screening or baseline purposes provided that the procedures met the protocol-specified criteria and were performed within the time frame defined in the SoA (Table 1).
- The study end-of-treatment assessments are to be conducted at the end of treatment or on the day of hospital discharge, whichever occurs later. The posttreatment follow-up assessment, conducted 30 days after the last dose of study drug (with a +7-day window), may be conducted either in the hospital or by telephone so that subjects do not have to be exposed to the hospital environment after hospital discharge.
- Discharged subjects will be provided with emergency study cards that include a list of symptoms associated with infections. The study card also guides subjects with instructions to contact their study physicians or seek emergency medical care in the event they experience any of the listed symptoms.

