# 7.3. Justification for Dose

A single bolus infusion of 180 mg of APL-9 followed by continuous infusion of 360 mg/day will be tested in this study. This will result in an initial dose of 540 mg of APL-9 in the first 24 hours of dosing (followed by 360 mg/day on all subsequent days). This dose and higher doses were well tolerated in a previous study in healthy volunteers and demonstrated comparable PK and complement inhibition to that in prior cynomolgus monkey studies. More detailed information can be found in the APL-9 Investigator's Brochure.

The purpose of this dosing scheme is to achieve rapid complement inhibition by APL-9 upon initiation of treatment, followed by a regimen selected to keep the complement system consistently suppressed for the duration of study drug administration. Discontinuation of dosing is expected to restore normal complement activity within 24 hours.

[figure not shown]

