- a Dosing must occur on Day 1, on the same day as randomization. The duration of subject participation in this trial may be variable. In Part 1, subjects may receive open-label treatment through Day 7 or resolution of ARDS (whichever occurs earlier). A DMC will review safety data from Part 1 and determine whether Part 2 can be initiated and whether Part 2 treatment can be extended beyond Day 7. Required criteria for initiation of Part 2 will include (1) no fatal/life-threatening SAEs thought possibly related to APL-9 by the DMC, and (2) no more than 1 subject requiring premature treatment discontinuation by the investigator due to AEs or abnormal laboratory tests. In Part 2, dosing may be extended only in subjects who still require respiratory support (oxygen supplementation or mechanical ventilation) at Day 7 with an improved PaO2/FiO2 ratio of at least 20 mm Hg from baseline if ABG test results are available for comparison. If ABG test results are not available, an improvement of FiO2 of at least 4% in nonventilated subjects (eg, those on nasal cannula) and 10% in mechanically ventilated subjects is needed. FiO2 should be weaned following the site's protocol to keep oxygen saturation at 89% or above. Treatment beyond Day 7 and through any DMC-approved extension will be at the discretion of the investigator. In Part 2, subjects will receive treatment up to and including the DMC-approved treatment duration, discontinuation of respiratory support (oxygen supplementation or mechanical ventilation), or hospital discharge (whichever occurs latest). Through Part 2, the DMC may review efficacy and safety data and recommend changes to the study conduct on an ongoing basis, but it will be required to review efficacy and safety data after the 10th and 30th subjects reach the DMC-approved treatment duration, discontinuation of respiratory support, or hospital discharge (whichever occurs latest). Enrollment will not be suspended during the DMC reviews. Subjects who reach the end of the approved treatment duration, discontinuation of respiratory support, or hospital discharge (whichever occurs latest) must be assessed as indicated in the EOT and discharge day column (for example, a subject who reaches the end of the approved treatment and achieves discontinuation of respiratory support on Day 6 should be evaluated with a radiograph or CT scan even though it is not indicated as a Day 6 assessment). All subjects will be followed up at the safety follow-up assessment 30 days after last study treatment (up to and including Study Day 51 with a +7-day window), either in person (for subjects still hospitalized) or by phone (for subjects who have been discharged).

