## 11.5. Pharmacokinetics

The exposure of subjects to APL-9 will be evaluated in serum from blood collected in a serum separator tube. Two serum aliquots of at least 0.5 mL will be stored at -70 °C and shipped on dry ice. Blood will be collected 3 times on Day 1: (1) once prior to administration of the APL-9 bolus, (2) once as soon as possible following the bolus (within 5-10 minutes) prior to the continuous infusion, and (3) once at 2 hours after the beginning of the continuous infusion. Blood will then be collected once daily between 1-2 hours after the first dose on Days 3, 5, 7, 11 (if treatment is ongoing), and 15 (if treatment is ongoing) and at the end-of-treatment visit. If the subject is discharged after the end-of-treatment visit, another sample will be collected on the day of discharge.

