## 11.6. Pharmacodynamics

The pharmacodynamic parameters evaluated in this study related to complement activation are levels of C3, C3a, Bb, C4, C4a, C5, and TCC) and AH50. The pharmacodynamic parameters evaluated in this study related to coagulopathy are reticulocyte count, presence of schistocytes, levels of D-dimer, ferritin, lactate dehydrogenase, haptoglobin, fibrinogen, CCl

The pharmacodynamic parameters evaluated in this study related to inflammation are levels of C-reactive protein (CRP), tumor necrosis factor  $\alpha$  (TNF $\alpha$ ), IL-1 $\beta$ , and IL-6. The complement activation markers and inflammatory cytokines will be analyzed in plasma from blood collected in K2 EDTA (dipotassium ethylenediaminetetraacetic acid) tubes with the exception of C-reactive protein, which is measured from serum. The AH50 hemolytic assay will be measured in serum from blood collected in red plain top (no gel) tubes. The coagulopathy markers will be analyzed in plasma collected in sodium citrate tubes or serum. These blood samples will be collected at the same time as the samples described in Section 11.5.

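### Protocol Section 11 and Table 1 disagree on the day of the end-of-treatment assessments, and SAP 12.4–12.5 do not keep off-drug PK/PD samples out of on-treatment visits

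*Protocol*

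**What the plan says.** Section 11 of the protocol gives one timing rule for the EOT assessments: "The study end-of-treatment assessments are to be conducted at the end of treatment or on the day of hospital discharge, whichever occurs later".

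Table 1 gives another. For the case where EOT and discharge fall on different days, footnote n tells the site to "perform EOT assessments on the last day of treatment and repeat on the day of discharge as an unscheduled visit". Footnote m is specific to PK/PD: "A PK/PD assessment will be done on the last day of treatment", and if discharge is on another day "a PK/PD sample will be collected on the discharge day as an unscheduled visit". Footnote a of the same table says that subjects reaching the latest of three events (end of approved treatment, end of respiratory support, discharge) "must be assessed as indicated in the EOT and discharge day column".

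Section 11.5 schedules PK blood on Days 3, 5 and 7, on Days 11 and 15 if treatment is ongoing, and at the EOT visit. It adds: "If the subject is discharged after the end-of-treatment visit, another sample will be collected on the day of discharge". Section 11.6 ties PD to the same draws: "These blood samples will be collected at the same time as the samples described in Section 11.5". On offset of effect, Section 7.3 says: "Discontinuation of dosing is expected to restore normal complement activity within 24 hours".

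SAP 8.1 and 9.1 summarise PK and PD by scheduled time point, with no condition that the subject is on drug. SAP 12.4 and 12.5 map unscheduled records into visit windows, again with no such condition.

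**The concern.** One visit label carries two timing rules. They agree when dosing runs to the day of discharge and differ whenever dosing stops earlier. That is foreseeable. In Part 1, treatment ends at Day 7 or at resolution of ARDS. In Part 2, Section 10.1 ends it at the maximum the DMC allows, even if the subject is still in hospital.

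For a drug whose effect is expected to disappear within a day, the choice of rule decides whether the EOT sample shows inhibition or recovery. APL-9 PK and the complement markers are secondary endpoints. If sites differ in the rule they follow, the EOT row mixes the two states, and its content depends partly on how long subjects stay in hospital after the last dose. The other items in the EOT column (SOFA, chest imaging, viral test) move with it, and the EOT viral test is an exploratory endpoint.

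**Working it through.** The plan states no figure on this point, so the check compares the texts and counts days.

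**Step 1: does another passage settle it?** Section 11 says that timings are summarised in Table 1 and requires adherence to it. But within Table 1, footnote a leans towards the later day while footnotes m and n name the last treatment day. Section 11.5 refers only to the EOT visit. Its provision for a further sample when discharge comes later has content only if the EOT visit can precede discharge. Under Section 11 it never can. So 11.5 fits footnotes m and n but does not itself fix the day. The amendment summary shows that the Section 11 wording and footnotes m and n all came in with Amendment 3, so neither rule can be dismissed as a leftover.

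**Step 2: days off drug at the EOT sample.** Let L be the last treatment day and D the discharge day. Under Section 11 the gap is max(L, D) − L. Under footnotes m and n it is 0. The documents give no discharge days, so D is assumed. Scheduled PK/PD days are 3, 5, 7, 11 and 15.

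| L | D (assumed) | Gap, Section 11 | Gap, footnotes m/n | Last scheduled draw on or before L |
|---|---|---|---|---|
| 7 | 7 | 0 | 0 | Day 7 (same day) |
| 7 | 8 | 1 | 0 | Day 7 (same day) |
| 7 | 12 | 12 − 7 = 5 | 0 | Day 7 (same day) |
| 14 | 17 | 17 − 14 = 3 | 0 | Day 11 (3 days earlier) |
| 21 | 24 | 24 − 21 = 3 | 0 | Day 15 (6 days earlier) |

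With Section 7.3's 24 hours, a gap of more than about one day turns an on-drug PD value into an off-drug one. When L is 7, the scheduled Day 7 sample still exists and only the EOT label is wrong. When L is 14 (the protocol's own example of an extension) or 21, Section 11 alone leaves no sample from the last treatment day.

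**Step 3: SAP windows, assuming the site follows footnotes m and n exactly.** I take the PK/PD sampling days as the visit targets; the SAP does not list the windows. SAP 12.4 sets bounds at midpoints and, for an even interval, gives the middle day to the later visit.

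- Days 7 and 11: midpoint (7 + 11)/2 = 9, interval 4, so Day 9 goes to Day 11.
- Days 11 and 15: midpoint (11 + 15)/2 = 13, interval 4, so Day 13 goes to Day 15.
- The Day 11 window is therefore Days 9–12.

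Take a subject with a last dose on Day 7 and discharge on Day 12. The Day 11 draw is planned only if treatment is ongoing, so that cell is empty. The Day 12 discharge sample is unscheduled, falls in the window, and under SAP 12.4 is used for Day 11. It is then summarised alongside anyone in that treatment group still being infused on Day 11.

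**The case against.** The strongest reply is that a careful site would not go wrong. Section 11 does not say that the assessments are done only once, and it sends the reader to Table 1, where the most specific instructions (m and n) require both draws. Under those, the EOT value is on drug. This stands to the extent that the EOT-row problem depends on some sites following Section 11. It does not remove the conflict, because footnote a points the other way, and it does not touch the window problem in Step 3.

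Second, the raw data allow samples to be sorted. Section 9.4 records the date, time and duration of each dose, Section 10.1 requires the time of termination, SAP 8.1 lists actual PK times with their deviation from nominal, and SAP 9.1 plots individual PD data at actual times. This is correct, and it makes the repair easy. But no planned summary uses those times to separate on-drug from off-drug samples.

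Third, the effect is confined to descriptive summaries and to subjects whose dosing ends before discharge. That also stands; the primary safety endpoint is unaffected.

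Three stronger readings are tempting and should be resisted. A reader might infer that Section 11.5 itself fixes the sample on the last treatment day; it does not. A reader might infer that on-drug information at the end of treatment is lost in general; a last dose on a scheduled sampling day keeps its sample. A reader might want a percentage bias in the mean concentration; that needs a half-life, a quantification limit and the share of sites following each rule, none of which the documents give.

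**Conclusion.** The concern holds as a current internal contradiction between Section 11 (with footnote a) and footnotes m and n, together with a separate gap in SAP 12.4–12.5. Its size can be stated only in days. Under Section 11 the EOT sample is off drug by the full interval from last dose to discharge, and under footnotes m and n by none. The harm to the EOT row is greatest when the last dose falls on a day with no scheduled sample. The Day 11 finding rests on my reading of the midpoint rule with PK/PD days as targets, and actual mixing requires that some subjects are still dosed on Day 11. Because PK and complement markers are secondary endpoints and the repair is small, it should be made, but it does not threaten the trial's main conclusion.

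**What to change.** **Protocol.** Reconcile the Section 11 bullet and footnote a with footnotes m and n: EOT assessments are done on the last treatment day and, if discharge is later, repeated then as a separately labelled discharge record. Make Section 11.5 name the day as well.

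**SAP.** In 8.1 and 9.1, restrict the EOT and on-treatment visit summaries of PK/PD to samples taken on treatment, identified from the recorded dose, stop and sample times. Report discharge samples taken after the last dose as off-treatment. In 12.4–12.5, exempt those samples from mapping into on-treatment visit windows.

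**Cost.** A short protocol clarification and a few SAP sentences. Footnote m already requires both draws, so no sample is added, and nothing about dosing changes.
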